8.1 Clinical Assessments

8.1.1 Concomitant Medications

All concomitant medication and concurrent therapies will be documented at Baseline/Screening and at visits 4, 5, and at early termination when applicable. Dose, route, unit frequency of administration, and indication for administration and dates of medication will be captured.

8.1.2 Medication Withholding

Bronchodilator reversibility will be used to establish eligibility at Visits 2, 5, and 8. Since some asthma medications can blunt the response to bronchodilators, we will ask that participants withhold these medications according to the guidance provided in Table 2.

Version #:1.5 Version Date: 8/5/2016 Page 20 of 41

Table 2. Medication Withholding Parameters

Medication	Withholding period
Leukotriene modifiers	24h
Ultra-long-acting bronchodilators (indacaterol, tiotropium)	24h
Long-acting beta-agonists	12h
Theophylline	12h
Short-acting anticholinergic	6h
Short-acting beta-agonists	4h

Participants will be evaluated at visit 1, without any medication holds, to establish the safety of withholding asthma medications. If a study clinician feels the participant is not clinically stable enough to withhold medications, they may shorten the guidance (with appropriate documentation on the Visit 1 CRF Physician Attestation section) or they may excuse the participant from some or all of the medication withholds.

Participants are reminded of these medication holds by phone 24 hours prior to their medication withholding visits and instructed to resume all medications should symptoms develop in the period prior to the visit.

Associated risks of medication withholding include a worsening of asthma control or asthma exacerbation. To mitigate these risks, participants are given clear instruction to resume asthma medications if symptoms arise.

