8 STUDY PROCEDURES AND GUIDELINES

A Schedule of Events representing the required testing procedures to be performed for the duration of the study is diagrammed in Appendix B.

Prior to conducting any study-related activities, written informed consent and the Health Insurance Portability and Accountability Act (HIPAA) authorization must be signed and dated by the participant.

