8.1.3 Food & Beverage Withholding

Participants are asked to withhold eating for our hour prior to sputum induction visits (2,5, and 8) and recently digested food can contaminate sputum samples. Participants are also asked to withhold caffeine and alcohol containing products for 6 hours prior to all study visits as these substances can influence lung function values.

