8.1.10 Post-Bronchodilator Reversibility

Spirometry will be repeated 15 minutes following the administration of four puffs of albuterol to assess bronchodilator reversibility. This procedure will be performed at visits 2-8.

Associated risks include the following:

- Likely (>10%)
 - · Transient tachycardia, tremor, feeling nervous, rhinitis, pharyngitis, and nausea.
- Less Likely (<5%)
 - · Headache, cough, upper respiratory infection.

- Rare but serious (<1%)
 - · Chest pain, atrial fibrillation, hypertension, hypotension, diabetic ketoacidosis, hyperglycemia, hypersensitivity reactions, paradoxical bronchospasm.

Given that the study population is made up of individuals with moderate-to-severe asthma, and that albuterol is a standard of care treatment for asthma, it is unlikely that participants will experience any of the side effects described above. However, if a potential participant describes previous sensitivity or side effects to treatment with albuterol, they will be excluded from participation for safety. Furthermore, albuterol will only be administered after a physician-administered history and physical, to ensure that it is okay for the participant to receive albuterol.

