9.4 Visit 4 (Day 5)

- 1. Record any adverse experiences and/or review participant diary for adverse experiences and exclusionary medication use.
- 2. Record changes to concomitant medications.
- 3. Perform abbreviated physical examination.
- 4. Perform and record vital signs.
- 5. Perform and record oximetry.
- 6. Perform and record urine pregnancy test.
- 7. Perform and record spirometry.
- 8. Perform and record post-bronchodilator spirometry.
- 9. Collect any unused study drug.
- 10. Review diary card.
- 11. Randomize if adherence is greater than or equal to 80% during run-in.
- 12. Provide education on use of personal nebulizer and administration of study medication.
- 13. Dispense study drug and initiate study diary.
- 14. Perform RN/MD supervised administration of first dose of nebulized study drug.
- 15. Schedule participant for Visit 5 in 7 days.

Version #:1.5 Version Date: 8/5/2016 Page 27 of 41

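### Section 8.1.2 ties the medication holds to Visits 2, 5 and 8, in conflict with section 8.1.10; read literally, the start and end FEV1 of each treatment period are measured under different withholding conditions

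*Combined protocol and SAP*

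**What the plan says.** Section 8.1.2 opens with "Bronchodilator reversibility will be used to establish eligibility at Visits 2, 5, and 8". It then explains that some asthma drugs blunt the bronchodilator response and asks participants to withhold them for the periods in Table 2 (4 to 24 hours by drug class). Visit 1 is the only visit expressly free of holds. The section treats the holds as belonging to particular visits: "Participants are reminded of these medication holds by phone 24 hours prior to their medication withholding visits".

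The holds are not absolute. A clinician may shorten them, with a note on the Visit 1 CRF, or "they may excuse the participant from some or all of the medication withholds". Participants are also "instructed to resume all medications should symptoms develop in the period prior to the visit".

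Section 8.1.10 gives a different visit list for the reversibility test: "This procedure will be performed at visits 2-8". The visit lists agree with 8.1.10. Visit 4 (section 9.4), for example, includes the step "Perform and record post-bronchodilator spirometry", and Visit 7 (section 9.7) has the same step.

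Section 14.3 defines the primary outcome as the percentage change in FEV1 over a treatment period. Period 1 runs from Visit 4 to Visit 5 and period 2 from Visit 7 to Visit 8. Section 14.4 adds the 7-day change on saline alone, and NAC responder bands (0-4, 5-9, 10-14 and above 15%) based on post-bronchodilator FEV1, which feed ROC curves for the CT mucus score.

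**The concern.** Two statements in 8.1.2 cannot stand. Visits 5 and 8 come after randomised treatment, so they cannot establish eligibility. And the three-visit list for reversibility disagrees with 8.1.10.

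The first matters little by itself. The second bears on the endpoint, because the hold request follows directly on the three-visit list. If site staff follow 8.1.2 literally, participants withhold bronchodilators and other asthma drugs before the last visit of each period but are not asked to before the first. The within-period change would then contain the effect of the hold as well as the effect of treatment.

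Any analysis that reads the change within one treatment would be exposed. That means the saline-only change, the NAC responder classes and the CT cut-off chosen from them.

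**Working it through.** **Step 1. Set the passages side by side.**

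| Visit | Role | Reversibility, 8.1.10 and visit lists | Named in 8.1.2 |
|---|---|---|---|
| 4 | start of period 1 | yes | no |
| 5 | end of period 1 | yes | yes |
| 7 | start of period 2 | yes | no |
| 8 | end of period 2 | yes | yes |

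No readable passage asks for a hold at Visits 4 or 7. For comparison, section 8.1.3 says outright that caffeine and alcohol are withheld before all study visits.

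**Step 2. The plan's own figure.** Section 14.6 gives SD 19, two-sided alpha 0.05, an effect of 10 and 80% power with 30 participants. Treating 19 as the SD of the quantity tested, n = (19 × (1.960 + 0.842) / 10)² = 28.3, so 29. By the noncentral t, power at n = 30 is 79.6%. The figure reproduces on that reading. It says nothing about holds.

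**Step 3. An illustration of size.** The documents give no hold effect. Assume that a hold at the end visit only lowers the measured change by h = 1 to 3 percentage points. From section 14.6 take SD 19 for a single-period change, n = 30 and a true mean NAC change of 10; take a true saline change of 0 and a normal distribution.

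*Responder share (change of 5% or more).* P = 1 − Φ((5 − (10 − h)) / 19).

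| h | share | expected of 30 | true change needed to be classed as a responder |
|---|---|---|---|
| 0 | 0.604 | 18.1 | 5 |
| 1 | 0.583 | 17.5 | 6 |
| 2 | 0.563 | 16.9 | 7 |
| 3 | 0.542 | 16.3 | 8 |

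*Saline-only change.* The mean reads −h, that is −1 to −3. The standard error is 19/√30 = 3.47, and the 95% CI half-width is 2.045 × 3.47 = 7.1. The shift is 1/7.1 = 0.14 to 3/7.1 = 0.42 of that half-width.

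*Primary paired difference.* If the drop is additive, (10 − h) − (0 − h) = 10.0. If the end value is instead lowered by a proportion h, the difference is 10 × (1 − h): 9.9 at 1% and 9.7 at 3%.

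**Step 4. Which FEV1.** The responder bands use post-bronchodilator FEV1, measured after four puffs of albuterol. A hold may change that value less than the pre-bronchodilator one, so the responder rows above may overstate the effect. Sections 14.3 and 14.4 do not say which FEV1 the primary and saline-only analyses use.

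**The case against.** The strongest answer is that the asymmetry may never have been intended.

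- The sentence requesting the holds names no visit. Its reason, a blunted bronchodilator response, applies at every reversibility visit, including Visits 4 and 7.
- The silence of the Visit 4 and 7 lists proves little, because the lists for Visits 2a, 5 and 8 do not mention holds either.
- The three-visit list looks borrowed. Section 8.1.3 attaches the same numbers to sputum: "sputum induction visits (2,5, and 8". It is unreliable even there: sections 8.1.12 and 8.1.14 give Visits 2, 5 and 8 for sputum and CT, yet the Visit 7 list in section 9.7 includes both.
- The governing schedule is elsewhere: "A Schedule of Events representing the required testing procedures to be performed for the duration of the study is diagrammed in Appendix B". Only its footnotes are readable here, and the grid may settle the matter.

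All of this stands, and it makes the mismatch conditional on a literal reading. It does not rescue 8.1.2. If holds were meant at every reversibility visit, its list is incomplete; if they were not, the FEV1 pairs are unequal. Either way the text needs correcting.

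It is also fair to say that hold departures are not wholly unrecorded. Shortened holds go on the Visit 1 CRF, a waiver decided there could apply alike to both periods, and medication changes are noted at Visits 4, 5, 7 and 8. But the diary asks for start and stop dates, whereas the holds run in hours. No readable passage asks staff to record at those four visits whether the hold was kept. The CRF itself is not among the documents, so such a field may already exist.

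**Conclusion.** The point holds as an internal conflict with a conditional consequence. Section 8.1.2 contradicts section 8.1.10 and mislabels Visits 5 and 8. Followed literally, it puts the two FEV1 values of each period under different withholding conditions.

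The consequence falls on secondary readouts. Under the assumed 1 to 3 point drop, about 0.6 to 1.8 of 30 expected responders would be lost and a null saline change would read −1 to −3. Both the size and the direction of the drop are assumptions.

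Two stronger conclusions are tempting, and the documents support neither.

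- A reader might infer that the primary NAC-saline comparison is biased. The same mismatch would occur in both periods, so a common shift largely cancels.
- A reader might infer a serious loss of power in that test. That needs the hold effect to vary independently between a participant's two periods. With an assumed SD of 5 or 10 points added to SD 19, power at n = 30 would be 74.3% or 60.9%, but nothing in the documents supports either value.

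**What to change.** Reconcile section 8.1.2, section 8.1.10, Appendix B and the lists for Visits 4, 5, 7 and 8 so that both visits of each pair (4 and 5; 7 and 8) are done under one stated withholding condition. Which condition that is remains the sponsor's clinical decision. Correct the description of Visits 5 and 8 as eligibility visits. At Visits 4, 5, 7 and 8, record whether the condition was kept, shortened, excused or broken by resuming medication, in addition to the Visit 1 CRF note on shortened holds.

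The cost is a protocol amendment with IRB approval, one CRF field if none exists, and possibly some participant burden or risk depending on the condition chosen (8.1.2 itself lists worsening of asthma control as a risk of withholding). No visit or test is added.

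A responder analysis on each participant's NAC-minus-saline change, in which a common shift largely cancels, is optional and not part of the fix. It would be as noisy or noisier: SD = 19 × √(2(1 − r)), which is 26.9 at an assumed within-person correlation r of 0 and 19.0 at r = 0.5.

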8.1.3 Food & Beverage Withholding

Participants are asked to withhold eating for our hour prior to sputum induction visits (2,5, and 8) and recently digested food can contaminate sputum samples. Participants are also asked to withhold caffeine and alcohol containing products for 6 hours prior to all study visits as these substances can influence lung function values.

8.1.4 Demographics

Demographic information (date of birth, gender, race) will be recorded at Screening.

8.1.5 Medical History

Relevant medical history, including history of current disease, other pertinent respiratory history, and information regarding underlying diseases will be recorded at Screening.

Associated risks include discomfort evoked with some of the questions asked. To minimize risk, participants will be informed that they can defer answering any questions that make them feel uncomfortable.

Version #:1.5 Version Date: 8/5/2016 Page 21 of 41

8.1.6 Physical Examination

A complete physical examination will be performed by either the investigator or a study clinician who is a physician at visit 1. Qualified staff (MD, NP, RN, and PA) may complete the abbreviated physical exam at all other visits. New abnormal physical exam findings must be documented and will be followed by a physician or other qualified staff at the next scheduled visit.

8.1.7 Vital Signs

Body temperature, blood pressure, pulse, and respirations will be performed after resting for 5 minutes at all study visits.

8.1.8 Oximetry

Oximetry will be measured on room air with the participant at rest at all study visits.

8.1.9 Spirometry

Spirometry will be performed at visits 1-8 in accordance with the current American Thoracic Society recommendations for the performance and interpretation of tests.

Associated risks include the following:

- Likely (>10%)
 - Shortness of breath or cough during the six-second exhalation part.
- Less Likely (<5%)
 - · Wheezing and chest tightness.
- Rare but serious (<1%)
 - Syncope

In an effort to minimize risk to participants will be seated during the procedure to reduce any injury should a participant become dizzy and fall. Coordinators will have albuterol available to administer to participants who develop wheeze or shortness of breath following spirometry.

8.1.10 Post-Bronchodilator Reversibility

Spirometry will be repeated 15 minutes following the administration of four puffs of albuterol to assess bronchodilator reversibility. This procedure will be performed at visits 2-8.

Associated risks include the following:

- Likely (>10%)
 - · Transient tachycardia, tremor, feeling nervous, rhinitis, pharyngitis, and nausea.
- Less Likely (<5%)
 - · Headache, cough, upper respiratory infection.

- Rare but serious (<1%)
 - · Chest pain, atrial fibrillation, hypertension, hypotension, diabetic ketoacidosis, hyperglycemia, hypersensitivity reactions, paradoxical bronchospasm.

Given that the study population is made up of individuals with moderate-to-severe asthma, and that albuterol is a standard of care treatment for asthma, it is unlikely that participants will experience any of the side effects described above. However, if a potential participant describes previous sensitivity or side effects to treatment with albuterol, they will be excluded from participation for safety. Furthermore, albuterol will only be administered after a physician-administered history and physical, to ensure that it is okay for the participant to receive albuterol.

8.1.11 Methacholine Challenge Testing

Methacholine challenge testing will be done according to the steps laid out in the UCSF Airway Clinical Research Center Methacholine Challenge Test Manual of Procedures (Appendix C). Only participants that are unable to achieve 12% improvement in FEV1% following administration of 4 puffs of albuterol and who have a baseline FEV1 >50% predicted will undergo methacholine challenge testing.

Associated risks include the following:

- Likely (>20%)
 - · Shortness of breath.
- Less Likely (< 20%)
 - · Wheezing, tightness, or cough.
- Rare but serious (< 1%)
 - · Rarely, patients may have severe bronchoconstriction during or following methacholine challenge.

Additionally, methacholine has been shown to increase tone of the uterus, which could lead to preterm labor, in pregnant laboratory animals; there are no human studies to verify this effect during human pregnancy. However, because of this, methacholine has been placed in FDA category C, meaning that exposure during pregnancy should be avoided. As such, pregnant women or women of reproductive age who are unwilling to practice pregnancy prevention strategies will be excluded from participation.

In an effort to minimize risk to participants, only those participants with a pre-diluent FEV1 of >50% predicted and at least one liter will undergo the methacholine testing, and only in the instance that they are not able to show 12% or greater improvement in FEV1 following bronchodilator administration. A study physician will be available during the challenge. Participants will not be discharged until their FEV1 is within 10% of their prediluent FEV1. Medications and personnel will be available to manage and treat bronchoconstriction.

8.1.12 Sputum Induction

A 12 minute sputum induction using 3% hypertonic saline will be performed at visits 2, 5, and 8. The procedure will be carried out according to the UCSF Airway Clinical Research Center Sputum Induction Manual of Procedures (Appendix C).

Associated risks include the following:

- Likely (>25%)
 - · Salty after taste in the mouth, coughing, or a feeling of needing to swallow.
- Less Likely (<5%)
 - Sore throat, shortness of breath, wheezing, chest tightness, light-headedness, nausea, or headache.
 - · Worsening of lung function.
- Rare but serious (<1%)
 - Some patients have had a severe asthma attack or a reaction to the salty water that they breathe in.

In an effort to minimize risk to participants, bronchodilator treatment will be available if sputum induction induces a worsening of asthma symptoms. The following safety procedures will be followed for the sputum induction procedure; only participants with a post-bronchodilator FEV1 of >50% predicted will undergo sputum induction, a physician will be available during the induction; study staff will calculate and record the peak flow and FEV1 value that equals both a 10% and 20% fall in lung function based upon the recorded post-bronchodilator peak flow and FEV1 values and participants will not be discharged until their FEV1 is within 10% of their post-bronchodilator FEV1.

8.1.13 Point of Care Urine Pregnancy Test

A point of care urine pregnancy test will be obtained from female participants who are of childbearing potential prior to their participation in the study and routinely throughout their participation (see Appendix B).

8.1.14 CT Imaging of the Thorax

A single inspiratory low dose CT scan of the thorax using a model based iterative reconstruction (MBIR) approach will be taken at baseline (visit 2) and following both treatment periods (visits 5 and 8).

The risks associated with CT scanning are that of the additional amount of radiation exposure. The additional amount of radiation that each participant will receive as a result of participating in this study will be approximately 4 mSv, which is slightly greater than the yearly natural background of radiation in the US, which is 3mSv. This amount of radiation may involve a low risk of cancer. A participant should not participate in this study if she is pregnant or breastfeeding.

Additional risks are associated with the uncovering abnormal findings. There is a risk of possible detection of an abnormality in the lung which, after testing or treatment, is found not to be disease-causing. This includes possible misdiagnosis of lung cancer. Such

Version #:1.5 Version Date: 8/5/2016 Page 24 of 41

findings may result in unnecessary anxiety for the participant, and increase his or her chance that an outpatient physician may believe that the abnormality is lung cancer and order further testing. This testing could include additional CT scans with additional radiation exposure, other types of scans to determine if the abnormalities are rapidly growing, a needle biopsy (taking a sample of the abnormality with a needle) or a lung biopsy which requires surgery. Whether these additional studies would be performed would be a decision that the participant would make with his/her regular physician.

In an effort to minimize risk to participants, scans will be read by radiologists that have expertise in interpreting findings of chest CTs. If there are any abnormalities, other than those that are usually found in asthmatic patients, observed by the clinical center radiologists, these will be reported to the principal investigator, who will in turn communicate these findings to the participant. The most likely abnormal result will be the identification of a spot on the lung that might be cancer.

8.1.15 Adverse Events

Information regarding occurrence of adverse events will be captured throughout the study. Duration (start and stop dates and times), severity/grade, outcome, treatment and relation to study drug will be recorded on the case report form (CRF).

8.2 Clinical Laboratory Measurements

8.2.1 Hematology

Blood will be obtained and sent to the clinical hematology lab for a complete blood count (hemoglobin, hematocrit, red blood cell count, white blood cell count, white blood cell differential, and platelet count), and serum IgE for assessment of systemic evidence for inflammation.

Risks associated with hematology include the following risks associated with venipuncture:

- Lightheadedness or nausea while having blood drawn
- Bruising at the site where the needle enters the skin and a remote risk of infection

In an effort to minimize risk to participants, aseptic technique will be used and pressure applied to site to prevent infection/bruising. Participants who have previously identified that they experience lightheadedness during blood draws will have blood drawn while lying supine on an exam room table.

8.3 Research Laboratory Measurements

8.3.1 Sputum Cell Count and Differential

Sputum for determination of total and differential cell counts will be collected at visits 2, 5, and 8. Specimens will be collected and processed according to the UCSF Airway Clinical Research Center Sputum Induction Manual of Procedures (Appendix C).

8.3.2 Sputum Cytokine Gene Expression Measurements

Sputum for determination of RNA gene expression of a number of airway-specific genes will be collected at visits 2, 5, and 8. Specimens will be collected and processed according

Version #:1.5 Version Date: 8/5/2016 Page 25 of 41

to the UCSF Airway Clinical Research Center Sputum Induction Manual of Procedures (Appendix C).

